2.2.2 Secondary Endpoints

Other measures of perinatal mortality including:

- Stillbirth at 28 weeks gestation and above (WHO definition of stillbirth)
- Stillbirth at 22 weeks gestation and above
- Stillbirth at 37 weeks gestation and above
- Stillbirths amongst normally formed infants of 22 weeks gestation and above, 24 weeks gestation and above, 28 weeks gestation and above and 37 weeks gestation and above
- Perinatal mortality (defined as stillbirth at 24 weeks gestation and above and deaths in the first seven days of life)
- Rates of caesarean section
- Rates of induction of labour (overall)
- Rates of elective delivery (induction of labour and caesarean section prior to the onset of labour) overall
- Rates of induction of labour at 39 weeks 0 days gestation or later
- Rates of elective delivery (induction of labour and caesarean section prior to the onset of labour) in women delivered at 39 weeks 0 days gestation or later
- Mean gestation at delivery for women having induction of labour

- Rates of admission to the neonatal unit (and their reasons)
- Rates of admission to the neonatal unit for more than 48 hours
- Rates of admission to the neonatal unit for term babies (those born at 37 weeks 0 days or greater)
- Proportion of women with fetal growth restriction (less than the 10th centile, customised for gender) remaining undelivered at or after 40 weeks gestation
- Rates of spontaneous vaginal delivery

Other secondary outcomes are the baby parameters:

- Gestation at delivery
- Proportion of babies born preterm (\leq 37 weeks and 0 days gestation)
- Sex baby
- Birthweight of baby
- Birthweight centile (according to the Intergrowth birthweight centile calculator at <https://intergrowth21.tghn.org>)
- Apgar score at 5 minutes
- Proportion of babies with 5 minute Apgar score $<$ 4
- Proportion of babies with 5 minute Apgar score $<$ 7
- Resuscitation required at birth

We will also collect the following data:

maternal age, maternity unit of delivery, birthweight, gestation of delivery, parity, gestation, sex, smoking (current and ever), maternal BMI, number of babies (one or more), ethnicity (to allow a customised birthweight centile to be generated), method of delivery, Scottish index of multiple deprivation (or other deprivation scores) (where available) other neonatal variables: Apgar score, resuscitation required at birth, encephalopathy etc.

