4 STUDY POPULATION

4.1 NUMBER OF PARTICIPANTS

Participants will be those delivering at all the sites described in Appendix 2 over the study period (36 months).

All eligible women will be recruited to the cluster RCT (Q1-4). Based on previous delivery numbers, after accounting for a washout period of two months (and assuming no withdrawals or losses to follow up) this is a total of around 300,000 women.

A subset of around 30 participating women and 30 midwives, sonographer and obstetricians will be recruited to address Q5.

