- If \geq 40 weeks, consider delivery within 48 hours as an alternative to USS.

ii If 27+0 – 36+6 weeks.

Assess for risk factors. Perform CTG within 2 hours and USS for LV within 12 hours.

- If CTG abnormal or LV reduced (deepest vertical pool \leq 2cm), involve senior obstetrician in management plan.
- If CTG and LV normal perform USS for EFW /AC next working day (+/- Dopplers as per local protocol).
 - If EFW/AC $>$ 10th centile, growth trajectory normal AND fetal movements have returned to normal discharge back to routine care.
 - If AC or EFW \leq 10th centile or there is decreased growth velocity or abnormal Doppler review by senior obstetrician as per local protocol for suspected FGR. The revised RCOG guidelines for SGA <http://www.rcog.org.uk/files/rcog-corp/GTG31SGA23012013.pdf> should also be consulted. Consider delivery by 37 weeks for women with suspected fetal growth restriction.

- If all normal but fetal movements have not returned to normal within 24 hours, follow recurrent reduced fetal movement pathway.

iii. If 24+0 – 26+6 weeks.

Assess for risk factors. Confirm fetal viability. Perform fetal anomaly scan if not already completed. If risk factors or FGR and stillbirth present, arrange serial growth USS as per local policy/RCOG guideline.

Recurrent episodes of reduced fetal movement.

Recurrent reduced fetal movement is defined as persistent reduced fetal movement for more than 24 hours or second or subsequent episode within 21 days of first presentation. If previous attendance \geq 21 days ago follow single episode guidance above.

iv. 37+0 weeks gestation or more

Perform CTG within 2 hours. Offer delivery (eg induction of labour) with input from senior obstetrician on timing (and certainly within 48 hours) if woman wishes delivery.

v. 27+0 – 36+6 weeks inclusive.

Perform CTG within 2 hours and LV within 12 hours of presentation. Schedule repeat USS scan for EFW/AC if it is \geq 21 days after previous USS (+/- Dopplers as per local protocol) and perform twice weekly CTG monitoring and weekly LV until then. Thereafter, manage according to repeat scan results. If measurements of EFW/AC are \leq 10th centile, or if there is decreased growth velocity, or abnormal Doppler review by senior obstetrician. If EFW/AC are $>$ 10th centile, return to routine care.

vi. 24+0 – 26+6 weeks inclusive.

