APPENDIX 5: AUDIT OF COMPLIANCE ADDED 17th July 2017

An audit of compliance with the affirm management protocol (appendix 4: updated 09/01/2015) for women presenting with reduced fetal movements will be determined by two means:

A) **QUESTIONNAIRE** Via Telephone or email contact with Principal Investigators at each site to determine which aspects of the AFFIRM protocol have been implemented effectively.

This will involve email contact with Principal Investigators to alert them to the request for information, detailing the information required, followed by a phone call to elicit the information (unless it had already been supplied). Investigators will be asked which of the following elements they had implemented locally:

- Issuing leaflets to all pregnant women,
- Cardiotocography within 2 hours of presentation,
- Measurement of amniotic fluid volume within 12 hours of presentation,
- Growth scan by the next working day for all women presenting with reduced fetal movement (and who had not had a growth scan within the last three weeks, or who were not being induced within 48 hours),
- Induction of labour within 48 hours for women presenting with recurrent reduced fetal movement at or after 37 weeks gestation.

Compliance (effective implementation) will be defined as 4/5 of the above management elements for 80% or more of the time.

AUDIT PART A: STAFF QUESTIONNAIRE

Dear (PI Name)

You very kindly agreed to answer some questions regarding your unit's compliance with the AFFIRM audit. We would be most grateful to receive your views on the following:

1. In your opinion, were the following aspects of the AFFIRM audit implemented at least 80% of the time at [Insert site name]?

Unit name: (Hospital name)	Yes	Partially	No	If Partially or NO, What proportion of women do you estimate received these?
Leaflets about RFM issued to women				
eLearning completed by staff				
CTG within 2 hours of presentation with RFM				
Growth scans for RFM (next working day)				
IOL for women 37 weeks and above with recurrent RFM (within 48hrs)				

2. If you could turn back time to 1st January 2014, and (with the benefit of experience) would you agree to participate in the AFFIRM study again? YES/NO

If NO, please could you explain why not?

We would be most grateful to receive your answers by **XX/ XXX/XXXX** If you haven't already given us your best address for sending out your vouchers, please don't forget to include this.

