## 5.2 Secondary:

The study secondary endpoints are:

- Stillbirth at 28 weeks gestation and above (World Health Organisation (WHO) definition of stillbirth: "a baby born with no signs of life at or after 28 weeks' gestation")
- Stillbirth at 22 weeks gestation and above: Delivery of dead fetus at or more than 22 weeks gestational age determined by weeks of pregnancy at delivery or gestational age at diagnosis of fetal death, if known; or birth weight of 500 grams or more, if fetal gestational age is not known.
- Stillbirth at 37 weeks gestation and above
- Stillbirth amongst normally formed infants of 22 weeks gestation and above, 24 weeks gestation and above, 28 weeks gestation and above and 37 weeks gestation and above (a normally formed infant is identified by the variable Fetal abnormality marker =No in the study dataset)
- Perinatal mortality (defined as stillbirth at 24 weeks gestation and above and deaths in the first seven days of life)
- Rates of caesarean section
- Rates of induction of labour (overall)
- Rates of elective delivery (induction of labour and caesarean section prior to the onset of labour) overall
- Rates of induction of labour at 39 weeks 0 days gestation or later
- Rates of elective delivery (induction of labour and caesarean section prior to the onset of labour) in women delivered at 39 weeks 0 days gestation or later
- Mean gestation at delivery for women having induction of labour
- Rates of admission to the neonatal unit (and their reasons)
- Rates of admission to the neonatal unit for more than 48 hours
- Rates of admission to the neonatal unit for term babies (those born at 37 weeks 0 days or greater)
- Birthweight centile (according to the Intergrowth birthweight centile calculator at <https://intergrowth21.tghn.org>)
- Proportion of babies with fetal growth restriction (defined as "being less than the 10th centile (customised for gender) and remaining undelivered at or after 40+0 weeks gestation)
- Rates of spontaneous vaginal delivery

Other secondary outcomes are the baby parameters:

- Gestation at delivery
- Proportion of babies born preterm ( $\leq 37$  weeks and 0 days gestation)
- Sex baby
- Birthweight of baby
- Birthweight centile (according to the Intergrowth birthweight centile calculator at <https://intergrowth21.tghn.org>)
- Apgar score at 5 minutes
- Proportion of babies with 5 minute Apgar score  $< 4$
- Proportion of babies with 5 minute Apgar score  $< 7$
- Resuscitation required at birth

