### **9.6.1 Stillbirth at 28 weeks gestation and above (WHO definition)**

### **9.6.2 Stillbirth at 22 weeks gestation and above**

### **9.6.3 Stillbirth at 37 weeks gestation and above**

### **9.6.4 Stillbirth amongst normally formed infants of 22 weeks gestation and above, 24 weeks gestation and above, 28 weeks gestation and above and 37 weeks gestation and above**

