**9.9.1 Discrete - Number of women presenting with decreased fetal movements**

**9.9.2 Continuous - Interval between perceiving fetal movements and presenting to hospital**

## **9.10 Exploratory Analyses**

Associations between intervention effects on outcomes will be investigated:

- Change in stillbirth rate; and change in the rate of inductions at or above 37 weeks gestation

- Change in stillbirth rate; and change in proportion of babies undelivered by 40 weeks + 0 days who are less than the 10th centile in birthweight

Associations will be presented graphically using one data point for each study site; where feasible a correlation summarising the association will also be calculated.

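### A birth at exactly 37+0 weeks is both preterm and term, because the preterm cut-off includes that day

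*Protocol*

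**What the plan says.** Protocol 2.2.2 includes among the baby parameters "Proportion of babies born preterm (\leq 37 weeks and 0 days gestation". SAP 5.2 repeats the outcome with the same cut-off. A few lines higher, both lists define the term group for another outcome: "Rates of admission to the neonatal unit for term babies (those born at 37 weeks 0 days or greater".

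Both outcomes are modelled. SAP 9.6 applies the primary-outcome method to each binary secondary outcome. SAP 9.6.13 is neonatal unit admission among term babies and restates the term cut-off. SAP 9.6.16 reads only "Proportion of babies born preterm", with no cut-off of its own, so the definition in SAP 5.2 is the operative one.

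Other uses of 37 weeks in the documents:

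- SAP 9.6.3: "Stillbirth at 37 weeks gestation and above"
- SAP 9.10: "change in the rate of inductions at or above 37 weeks gestation"
- Protocol Appendix 4, recurrent episodes: "37+0 weeks gestation or more", with the band below it ending at 36+6
- Protocol Appendix 5, compliance audit: "Induction of labour within 48 hours for women presenting with recurrent reduced fetal movement at or after 37 weeks gestation"

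Neither document says how a birth at exactly 37+0 is to be assigned.

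**The concern.** Preterm and term should divide births at one point. Here the two definitions share a day, and the plan's other cut-offs all treat that day as belonging to the later group.

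A statistician who follows SAP 5.2 literally will report as preterm some babies whom SAP 9.6.13 counts as term. The published proportion would then not be comparable with one that stops at 36+6. A statistician who instead codes preterm as before 37+0 will depart from the prespecified definition, possibly without any record of it. At stake are the level and the meaning of one modelled secondary outcome.

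**Working it through.** **Is the overlap real?** Express gestation in days, with 37+0 = 7 × 37 = 259.

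- Preterm as written (Protocol 2.2.2, SAP 5.2): g ≤ 259.
- Term as written (same lists, and SAP 9.6.13): g ≥ 259.
- Intersection over 22+0 to 42+6: the single day 259, that is 37+0. No day is left unclassified.
- With preterm as g < 259, the last preterm day is 258 (36+6), the intersection is empty, and there is still no gap.

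**Could the sign be an error of text extraction?** This is unlikely. The less-than-or-equal sign appears in both documents, while the Apgar cut-offs in the same lists are read as strictly less than. The text therefore keeps the two signs apart.

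**Which definition is out of line?** The two outcome cut-offs (term neonatal admission, stillbirth from 37 weeks), the exploratory induction rate, the Appendix 4 bands and the Appendix 5 audit criterion all put 37+0 on the upper side. Only the preterm definition puts it on the lower side.

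**How large is the effect on the reported figure?** The plan gives no figure to reproduce. The only input from the documents is the number of deliveries after washout in Protocol 4.1: "this is a total of around 300,000 women". Two inputs are assumptions:

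- s, the share of births on exactly 37+0: 0.4% to 1.5%
- t, the share of births before 37+0: 6% to 8%

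The formulas are:

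- Births meeting both definitions = 300,000 × s
- Relative rise in the preterm proportion = s / t
- Share of the reported preterm group born on 37+0 = s / (s + t)

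| s | t | Births in both | s / t | s / (s + t) |
|---|---|---|---|---|
| 0.4% | 8% | 1,200 | 5.0% | 0.4 / 8.4 = 4.8% |
| 1.0% | 6% | 3,000 | 16.7% | 1.0 / 7.0 = 14.3% |
| 1.5% | 8% | 4,500 | 18.8% | 1.5 / 9.5 = 15.8% |
| 1.5% | 6% | 4,500 | 25.0% | 1.5 / 7.5 = 20.0% |

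In absolute terms the preterm proportion rises by s, that is 0.4 to 1.5 percentage points, in both phases. The 300,000 counts women, whereas the ITT population in SAP 8.1 counts babies, so the number of births would be slightly higher once multiple births are included.

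**A further possibility.** The documents do not say whether every regional source records gestation in weeks and days. If one holds completed weeks only and the outcome is coded as 37 or less, the overlap widens from one day to seven (37+0 to 37+6).

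**The case against.** The best defence is that nothing in the analysis needs preterm and term to be mutually exclusive. SAP 9.6.16 is a proportion of all babies, and SAP 9.6.13 is an admission rate among babies born at 37+0 or later. They are separate models, and no single outcome counts a baby twice. A cut-off applied identically in both phases gives a valid estimate of the effect on the outcome as defined. Preterm birth is listed among the baby parameters, and none of research questions Q1 to Q6 asks about it. The sizes above depend on assumed shares, and the Appendix 4 and 5 cut-offs are management and audit criteria, not outcome definitions.

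All of this stands, and it keeps the point minor. It does not remove the inconsistency. The two outcome definitions in the same list still disagree about 37+0, and the figure reported as preterm would include babies whom the plan elsewhere calls term. The mean gestation comparison in SAP 9.7.2 does not fill the gap, because a difference in means does not show how many births fall on one day.

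**Conclusion.** The point holds as a minor error in an outcome definition. The one-day overlap is certain from the text. Its size is not: under the assumed shares, about 5% to 20% of babies reported as preterm would have been born on 37+0, and the reported proportion would be 5% to 25% higher in relative terms than one that stops at 36+6. No shift in the odds ratio is claimed. The primary stillbirth analysis, the power calculation and the term neonatal admission model are unaffected.

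**What to change.** In SAP 5.2, define preterm as born before 37 weeks and 0 days (36+6 or earlier), and restate that cut-off in SAP 9.6.16. If any source holds completed weeks only, state there that preterm means 36 completed weeks or fewer.

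Make the change in a signed SAP version before the randomisation list goes to the analysing statistician under SAP 7.5. The documents do not show whether that has already happened; if it has, date the correction and declare it in the statistical report.

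Align Protocol 2.2.2 at the next amendment. Under Protocol 13.1 this needs chief investigator and sponsor approval and written submission to the REC and local R&D, so it is best carried with other changes.

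The cost is two edited SAP lines and a sign-off. Gestation at delivery is already collected, so no new data are needed. Only an outcome definition changes; no clinical threshold in Appendix 4 is affected.

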3 STUDY DESIGN

This is a multicentre, stepped wedge cluster randomised trial of a package of care consisting of a management plan for identification and delivery of the 'at risk' fetus, together with strategies for increasing pregnant women's awareness of the need to report decreased fetal movements early. A nested qualitative study will examine the acceptability of the intervention to patients and health care providers and identify process issues (barriers to implementation). Clinical audit (before and after the change in practice) will be used to determine the effect of interventions on process outcomes (eg number of ultrasound scans, number of admissions for induction of labour). The study will take place in participating hospitals in the UK.

The interventions will be introduced over a 33 month period. Data will be collected over a 36 month period.

Data in the 'active phase' after introduction of the intervention will be compared to data in the 'control phase' – the time from study start to the time of introduction of the intervention. Given

that it will take individual units some time (a) to effect change in management in their unit from time of introduction of the intervention and (b) that it will take some time for this change in practice to impact on clinical outcomes, we plan a “washout” period after the introduction of the intervention during which data will not be included in either group for analysis. We anticipate that this washout period will be of two months duration – this will be finalised in the statistical analysis plan.

Outcomes will be measured from routinely collected data. For consistency, we will normally only include data items which become available within four months after the delivery date in question, although we may seek advice from the TSC about exceptions as they arise.

A diagram indicating randomisation of hospital groupings in the stepped wedge design is shown below:

Table 1: Stepped wedge design. Shaded areas indicate periods in which the interventions are being implemented. The order in which hospital groupings implement the interventions will be determined via randomization.

Hospital groupings	Month								
	1-4	5-8	9-12	13-16	17-20	21-24	25-28	29-32	33-36
1-3									
4-6									
7-9									
10-12									
13-15									
16-18									
19-21									
22-24									

This is a cluster randomised trial and individual patient consent is not required for the package of care. However, participants’ will be asked to sign a study specific ethically approved consent form for the qualitative interviews which are planned with both women and health care professionals. . There are no stopping rules for the study.

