4.3 EXCLUSION CRITERIA

We will exclude women as follows:

- Women for whom data on delivery outcomes is still unavailable four months after the date of delivery

- Women delivering in the “washout” period in each unit.

Members of the trial management group and participants who do not speak/understand English will be excluded from those participating in Q5.

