The power actually achieved in the study will be slightly lower, as deliveries during the two month “washout” period following implementation of the intervention in a site will not be included in the analysis. The effect of this was explored using the Stata function steppedwedge (27), which showed the statistical power would become 88.2% (30% risk reduction) and 74.6% (25% risk reduction). It is anticipated that unavailability of data and women asking to withdraw their data will be less than 1%.

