### 3.2 Definitions

Throughout the reporting of the study, the studied interventions will be reported as “Active Phase” and “Control Phase”, and will be collectively referred to as the Intervention groups.

Study time periods in this step wedge design will be defined as period 1 (1 to 4 months), period 2 (5 to 8 months), etc., until period 9 (33 to 36 months)

Two calendar months will be manually determined once the date for “Active Phase” and “Control Phase” are provided by the study team (i.e. for the 28 February 2015, two calendar months later will be 28 April 2015).

For all data, where applicable clinical visits/observations will be referred to as: delivery, 7 days post-delivery, between 7 days and 28 post-delivery and between 28 days and 1 year post-delivery.

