## 4 Study Design

### 4.1 Brief Description

AFFIRM is a pragmatic, multi-centre, stepped wedge cluster design trial, in which participating hospitals in the UK will be randomized to the timing of introduction of a care package. The tested intervention is a package of care consisting of a management plan for identification and delivery of the ‘at risk’ fetus, together with strategies for increasing pregnant women’s awareness of the need to report decreased fetal movements early.

Data in the ‘Active Phase’ after introduction of the intervention will be compared to data in the ‘Control Phase’. There will be a washout period of two calendar months after the introduction of the intervention commences during which data will not be included in either group for analysis. Outcomes will be measured from routinely collected data.

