### 9.5 Primary Outcome

The primary outcome will be summarised overall, and by study site and active/control periods expressed as a rate per 1000 live births. Number of stillbirths (CEMACH definition) will be analysed on an intention to treat basis, incorporating all patients in the ITT population for whom outcome data are available. The number of stillbirths will be compared before and after implementation of the Active intervention using a logistic regression generalised linear mixed model following the model structure described in Hussey and Hughes [3]. The effect of implementation of the Active intervention will be presented as an odds ratio and its 95% CI. The intervention groups will be ordered in such a way that an odds ratio of less than one corresponds to a benefit for Active Phase over Control Phase

The event rate  $\mu_{ij}$  in site  $i$ , study period  $j$  will be modelled in the linear component of the logistic regression as:

$$\mu + \alpha_i + \beta_j + \theta X_{ij}$$

where:  $\mu$  is the overall mean event rate on the logit scale;

$\alpha_i$  is a zero-mean random effect for site  $i$ ,  $\alpha_i \sim N(0, \tau^2)$ ;

$\beta_j$  is the fixed effect log-odds ratio for time period  $j$ , with  $\beta_1=0$  for identifiability;

$\theta$  is the fixed effect log-odds ratio for the intervention;

$X_{ij}$  is a (0/1) variable to indicate whether the intervention is implemented in site  $i$  during period  $j$ .

A site by intervention interaction random effect will be included in the model and retained if it is found to explain an important proportion of the variability in outcomes.

The patient-level covariate included will be maternal age and number of babies (one; more than one).

A secondary analysis adjusting for a full list of patient-level covariates will also be included (maternal age, parity, smoking status during pregnancy, maternal BMI, number of babies (one or more) and ethnicity). This will be performed as a complete-case analysis.

A further secondary analysis not adjusting for patient level covariates will also be performed.

Also, a Scotland only model will be generated with the patient-level covariates included in the primary analysis plus the deciles of deprivation.

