**9.6.13 Rates of admission to the neonatal unit for term babies (those born at 37 weeks 0 days or greater)**

**9.6.14 Proportion of babies with fetal growth restriction**

**9.6.15 Rates of spontaneous vaginal delivery**

**9.6.16 Proportion of babies born preterm**

## **9.7 Continuous Secondary outcomes**

For the following continuous outcomes a mixed linear regression model will be used to compare the means between the intervention groups adjusting by a random effect for site and fixed effects for the intervention implementation and study time periods. The result will be presented as an adjusted difference in means together with its corresponding 95% CI and p-values:

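### The two-month washout does not line up with the SAP's four-month period effects, so about a third of one month's secular trend enters each modelled intervention effect; the bias is small and cheap to remove.

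*Protocol*

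**What the plan says.** Protocol section 3 sets aside births after introduction of the package, "during which data will not be included in either group for analysis". SAP 4.1 fixes the length: "There will be a washout period of two calendar months after the introduction of the intervention commences". The exclusion is specific to the unit that is crossing over. Protocol 4.3 words it as "Women delivering in the “washout” period in each unit".

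Protocol 8.1 and Table 1 have three hospital groups stepping every four months, eight steps in all, with data over 36 months.

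On time adjustment, SAP 3.2 says that study time periods "will be defined as period 1 (1 to 4 months), period 2 (5 to 8 months" and so on, up to period 9. In the primary model of SAP 9.5 the time term "is the fixed effect log-odds ratio for time period" j, next to a 0/1 indicator by site and period. There is no within-period time term. SAP 9.6 carries this model to the binary secondary outcomes. SAP 9.7 uses a linear mixed model for three continuous outcomes, "adjusting by a random effect for site and fixed effects for the intervention implementation and study time periods".

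Protocol 8.1 gives the planned power after the washout: "the statistical power would become 88.2% (30% risk reduction) and 74.6% (25% risk reduction").

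**The concern.** A stepped-wedge model separates the intervention from calendar time by comparing active and control births within the same period. That works if births in a period are spread over the same dates in every group. Here they are not. In its crossover period a stepping group has lost months 1 and 2 to the washout and supplies only months 3 and 4, all active. The other 21 groups supply months 1 to 4. One flat effect per period cannot absorb the difference in timing.

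The shift has the same direction at all eight steps, so it does not average out, randomising the order does not remove it, and more births do not shrink it. A rising background rate is partly counted as an effect of the package, and so is a falling one.

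The outcomes that matter here are the common ones. Whether the package raises caesarean section and induction is a stated secondary objective (Protocol 2.1.2, Q2). With about 300,000 births their standard errors are small.

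**Working it through.** **Inputs from the documents.**
- 24 equal groups, three per step, steps at months 5, 9, ..., 33 of 36; two months dropped after each step.
- Deliveries: (58,000 + 50,000) / (24 × 12) = 375 per group-month. Total 24 × 36 × 375 = 324,000, less 24 × 2 × 375 = 18,000, leaves 306,000. Protocol 4.1 says about 300,000.
- Baseline stillbirth rate p0 = 0.438%, between-cluster coefficient of variation (CV) 0.333, two-sided 5%.

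**Assumptions, not in the documents.** Crossovers at period boundaries; linear trend; induction rate 28%, rising 4 to 10% a year in relative terms; for induction, CV 0.10 to 0.30 and a site-by-intervention SD of 0 to 5% of the rate.

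**Step 1. Reproduce the stated power.** Hussey-Hughes generalised least squares on monthly cells, with within-cell variance p0(1 − p0)/375 and between-group SD 0.333 × p0. Power = Φ(relative reduction / relative SE − 1.96).

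| Design | Relative SE | 30% reduction | 25% reduction |
|---|---|---|---|
| No washout | – | 92.4% (stated 92.4%) | 80.6% (stated 80.7%) |
| Washout, two-month or monthly effects | 0.0954 | 88.2% (stated 88.2%) | 74.6% (stated 74.6%) |
| Washout, four-month effects | 0.0949 | 88.5% | 75.0% |

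For the second row, 0.30/0.0954 − 1.96 = 1.18, and Φ(1.18) = 0.88.

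**Step 2. Misalignment.** Mean month within the crossover period: stepping group (3 + 4)/2 = 3.5; other groups (1 + 2 + 3 + 4)/4 = 2.5. The gap is 1.0 month. It arises once per group, in 24 of 24 × 9 = 216 group-periods.

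**Step 3. Share of trend reaching the intervention effect.** Applying the same estimator to calendar month t gives L, the intervention element of (X′V⁻¹X)⁻¹X′V⁻¹t. The bias is L × the change per month.
- Four-month effects: L = 0.33 for stillbirth, about 0.37 for induction, and up to 0.41 with the site-by-intervention term.
- Two-month or monthly effects: L = 0.
- Cross-check: a logistic fit to expected counts with a log-odds trend of 0.08 a year gives a bias of 0.0025 with four-month periods, that is 0.0025/(0.08/12) = 0.375 month, and 0.0000 with two-month periods.

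**Step 4. Size.**
- Stillbirth, 10% a year: 0.333 × 0.10/12 = 0.0028 on the log scale. Divided by 0.0949, this is 0.029 SE. A fall of that steepness multiplies the odds ratio by 0.997.
- Induction, 4% a year: 28 × 0.04/12 = 0.093 percentage points a month; × 0.37 to 0.405 = 0.03 to 0.04.
- Induction, 10% a year: 28 × 0.10/12 = 0.233 points a month; × 0.37 to 0.405 = 0.086 to 0.094.
- The SE is 0.30 points without the site-by-intervention term and 0.42 with it. The larger L goes with the larger SE, so the bias is 0.09 to 0.29 SE.
- Rejection rate Φ(−1.96 + z) + Φ(−1.96 − z): 5.1% at z = 0.09 and 6.0% at z = 0.29.

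**Step 5. Crossovers off the boundary.** If they fall one month off, four-month effects leak 0.53 to 0.59 month and two-month effects 0.17 to 0.18. Monthly effects leak none when crossovers fall at the start of a month, and about 0 to 0.05 month otherwise.

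**The case against.** The strongest reply is that this is a refinement with little practical effect. Time effects that match the four-month steps follow the model structure that the SAP cites. Each group is affected in one period of nine, and its comparators include births from the same months 3 and 4. The primary conclusion does not move: the trial is powered on a 25 to 30% reduction, against an odds-ratio shift of about 0.3% for a 10% yearly trend. The induction figures rest on a rate and a trend that the documents do not give. All of this stands, and it is why the point is minor. It does not remove the mechanism, which follows from the documents alone. The time-lag exploration in SAP 9.5.1 does not cover it either, since it concerns build-up or fading of the effect and not calendar time within a period.

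Three stronger readings are tempting and are not supported.
- A reader might infer that half of every period is lost, or that every reported result is affected. The washout is unit-specific, and the process outcomes and several baby outcomes are only summarised in the SAP, with no model.
- A reader might infer from Step 1 that the SAP model is not the one that was powered. The gap is 0.3 to 0.4 points, and the delivery numbers are rounded: at 371 births per group-month, about 1% fewer, four-month effects also give about 88.2% and 74.6%.
- A reader might set the induction bias against the 0.4 to 1% increase in Protocol Appendix 4. That figure is a worst case that assumes presentations double, not an expected effect, so the ratio would say little. The standard error is the better yardstick.

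**Conclusion.** The point holds as a minor specification issue. Under the planned schedule, 0.33 to 0.41 of one month's secular change enters each modelled intervention effect, with the sign of the trend. For stillbirth this can be ignored. For a common modelled outcome it is small but systematic: up to 0.09 percentage points, or 0.29 standard errors, at the steep end of the assumed induction trend. The mechanism needs only the documents. The sizes depend on equal groups, crossovers at period boundaries, a roughly linear trend, and the assumed induction rate, trend and variance components. A flatter trend shrinks the bias in proportion, and with no trend there is none.

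**What to change.** In SAP 3.2, and so in 9.5 to 9.7, define study time for the model as calendar months, giving 36 time effects instead of nine. Leave the steps, the washout and Table 1 as they are.

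Two-month periods would also remove the leak, but only if every crossover falls on a two-month boundary. SAP 3.2 determines the washout dates by hand once the phase dates are known, and 9.4 allows for implementation at times other than those randomised, so monthly effects are safer. If they prove unstable for the rarest stillbirth outcomes, use two-month periods there and say so in the SAP.

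The cost is 27 more fixed effects (36 − 9) on about 300,000 births and a standard error 0.3 to 0.6% larger. Power stays at the protocol's 88.2% and 74.6%. Under SAP 7.5 the randomisation list is released to the analysing statistician only after the SAP is signed off, so the change belongs before that point.
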